Short Title / Study ID:	Receptive Fields and their stimulation, RKB-SMR-01		
Protocol Version and Date:	Protocol Version 02, 10.10.2017		
Trial registration:	The study is intended to be registered on the SNCTP (automatically through this application) and before initiation of the project also in a WHO primary register (ClinicalTrials.gov)		
Study category and Rationale	Clinical investigations or other studies of medical devices, risk category A. This study is a clinical evaluation as it involves the direct testing of patients. The risk category A is justified as the medical device bears a conformity marking, and is used in accordance with the instructions.		
Clinical Phase:	Descriptive study of the receptive fields and phase of final evaluation of efficacy on patients of the stimulation system.		
Background and Rationale:	It has been observed that patients subjected to amputations develop so called receptive fields, which time of occurrence and localization over time are yet not examined systematically. A receptive field is defined as skin area anywhere on the same side of the body as the amputation, which when stimulated by others, causes phantom sensations in the amputated extremity. Furthermore, a device has been developed and certified, which can stimulate these receptive fields, and though evoke those sensations, through conventional TENS-Electrodes.		
Objective(s):	This clinical trial aims to investigate the reliability in detecting these receptive fields as well as their incidence and changes over time. Further it aims to evaluate the acute effect of the stimulating system ("Phantom Stimulator" (Cort X Sensorics, Spaichingen, Germany)) on selected gait parameters measured tough a gait analysis system ("OprtoGait" (Microgate, Bolzano, Italy)) as well as on phantom sensations measured through a questionnaire.		

Outcome(s):	The primary outcomes are the changes in size and position over time and their timed occurrence after the amputation of these receptive fields as well as the inter-/intratester reliability in their detection. The secondary outcomes are the change in selected gait parameters and phantom sensations through the application of the stimulating system ("Phantom Stimulator" (Cort X Sensorics, Spaichingen, Germany)).		
Study design:	The primary outcome is of mere descriptive nature. Therefore, no control group is created and the participants are not blinded or randomized. For the secondary outcomes, every tested subject serves as its own control (cross over). The gait analysis as well as the questionnaire are performed three times. The two measurements after the first familiarization measurements are performed in a randomized order.		
Inclusion / Exclusion criteria:	 Inclusion criteria for descriptive study: Lower limb amputation (independently of side or height of amputation) Inclusion criteria for Phantom stimulator: Receptive fields present at testing day 31 (last regular assessment of the receptive fields) Lower limb amputation below the knee (if both sides the system is applied to the dominant side) Exclusion criteria: Implanted devices (defibrillator or pacemaker) Pregnancy 		

Measurements and procedures:	Before enrollment into the study, the possibility of participation is assessed through an internal screening of the database of the Rehaklinik Bellikon as well as through a telephonic/personal				
	Interview with the interested people. A Pregnancy test is also conducted.				
	Receptive Fields:				
	After the inclusion into the study the procedures are planned as follows:				
	-Day 1: detection of the receptive fields by one single tester at a self-selected time of day.				
	-Day 2: detection of the receptive fields at the same time of d on day 1 by the same tester as on day 1.				
	-Day 7: detection of the receptive fields at the same time of day as on day 1 by the same tester as on day 1.				
	-Day 14: detection of the receptive fields at the same time of day as on day 1 by another tester as on day 1				
	as on day 1 by another tester as on day 1. -Day 21: detection of the receptive fields at the same time of day as on day 1 by the same tester as on day 1				
	-Day 28: detection of the receptive fields at the same time of day as on day 1 by the same tester as on day 14				
	-Day 31: detection of the receptive fields at the same time of day as on day 1 by the same tester as on day 1.				
	The expression "same time of day" stands for: -at maximum 1-hour difference in timing between the measurements.				
	-similar sleeping and dietary pattern 12 hours prior the measurement (assessed through a questionnaire).				
	 The detection of the receptive fields is planned as follows: 1. performed by two specifically trained testers 2. performed through tactile stimulation of the skin surface with a brush (mild toothbrush or similar) 				
	 the receptive fields are determined through the dialogue with the participant. Here he can signal the presence of a receptive field with the word "Yes". Important in this setup is that the participant does not look at the inspected site or the tester. 				
	 the receptive fields are drawn on to the skin with a commercial eveloper papel. 				
	 the drawn receptive fields are photographed from different locations under standardized conditions (distance and angle) 				

 this photo is imported in the program Photoshop (Adobe Photoshop Version 2017.1.1) where the respective area and position can be determined.
This testing Phase consists of 7 meetings of approximatively one hour. Therefore, the expenditure of time is of approximatively 7 hours over one month.
Phantom Stimulator:
Participants qualifying for the Phantom Stimulator are tested within 1 week after day 31. These tests are performed on one single half-day. Therefore, the expenditure of time for this phase is of approximatively 4 hours. The "Phantom Stimulator is worn for approximatively 3 hours during that phase.
 This day is planned as follows: -first (for familiarization): Walking for 1000 Steps with a step counter, questionnaire and 10 runs of gait analysis -second: The Phantom Stimulator (Cort X Sensorics, Spaichingen, Germany) will be installed -third: Participants will perform A or B in a randomized and balanced order: A. walking with the functioning (ON) Phantom Stimulator (1000 steps), questionnaire and 10 runs of gait analysis B. walking with the unfunctional (OFF) Phantom Stimulator (1000 steps), questionnaire and 10 runs of gait analysis
 For gait analysis, subjects will be walking in maximally possible self-selected speed for 10 runs (both directions are analyzed). The recorded parameters during the gait analysis are: Step width Step length Ground contact time Cadence Walking speed
The 1000 steps during the familiarization and testing phases are recorded/controlled through a pedometer (Omron Walking Style One 2.0, Mannheim, Germany).

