3. BACKGROUND AND RATIONALE

3.1 Background and Rationale

It has been observed that patients subjected to amputations develop so called receptive fields (observations at Rehaklinik Bellikon and Cort X Sensorics), which time of occurrence and localization over time are yet not examined systematically.

A receptive field is defined as skin area ipsilateral to the amputation, which when stimulated by others, causes phantom sensations in the amputated extremity. Phantom Sensations are defined as sensations originating from a body part not connected through the nervous system.

Furthermore, a device has been developed and certified, which can stimulate these receptive fields, and though evoke these sensations, through conventional TENS-Electrodes.

The questions to be answered in the first part of the study are the changes in size and position over time and their timed occurrence after the amputation of these receptive fields as well as the inter-/intratester reliability in their detection.

The testing sequence is explained in sections Study Synopsis and Study Schedule. The monitoring of these fields, which entails no harms to the participants, enables the correct use of the followingly tested stimulation system (Phantom Stimulator, Cort X Sensorics, Spaichingen, Germany) and therefore entails all its benefits.

The question to be answered in the second part of the study is whether in people with lower limb amputation below the knee (prosthesis cannot entail an artificial knee) a "Phantom stimulator" (Cort X Sensorics, Spaichingen, Germany) produces a measurable effect. This effect is measured through changes in gait parameters (gait analysis with OptoGait) and a self-elaborated questionnaire concerning phantom sensations. As above, the testing sequence is described as well in the sections Study Synopsis and Study Schedule.

This treatment constitutes a supplement to the today normally used prosthetic treatment as it upgrades the patient's normal prosthesis by adding a sensory insole, a black box and electrode patches.

Studies investigating the use of this product haven't been done so far, yet important findings have been made regarding the reduction of phantom limb pain thanks to enhanced sensory input from the lost extremity.

- Katz J. (1991); Auricular Transcutaneous Electrical Nerve Stimulation (TENS) reduces Phantom Limb Pain; Journal of Pain and Symptom Management 6 (73-83)

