7. STUDY POPULATION

7.1 Eligibility criteria

Participants fulfilling all the following inclusion criteria are eligible for the first part of the study:

- Informed Consent as documented by signature (Appendix Informed Consent Form)
- Lower limb amputation
- Legal age, capable of judgement

Participants fulfilling all the following inclusion criteria are eligible for the second part of the study:

- Lower limb amputation below/distal of the knee
- Presence of receptive fields for heel and forefoot at day 31 of the first part of the study

The presence of any one of the following exclusion criteria will lead to exclusion of the participant from the entire study:

- With history or suspect of non-compliance, drug or alcohol abuse
- Inability to follow the procedures of the study, e.g. due to language problems, psychological disorders, dementia, etc. of the participant
- Participation in another study with investigational drug within the 30 days preceding and during the present study
- Previous enrolment into the current study
- Enrolment of the investigator, his/her family members, employees and other dependent persons

The presence of any one of the following exclusion criteria will lead to exclusion of the participant from the second part of the study:

- Contraindications to the product under investigation (skin irritability or allergy to electrode glue)
- Women who are pregnant or breast feeding
- Intention to become pregnant during the study
- Implanted devices as pacemakers or defibrillators

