7.2 Recruitment and screening

The study participants are preselected through a database of the Rehaklinik Bellikon and run per all in- and exclusion criteria. As a second step, the selected patients are contacted via E-Mail or personally if stationary at the Rehaklinik Bellikon. A pregnancy test is also conducted.

The preselection can be performed by every employee of the Rehaklinik Bellikon as he/she must have access to the patient information program. The second step of the contact via E-Mail, is performed through a separately created E-Mail address ([contact]) and can therefore be performed by authorised personnel only ([name] and [name]). Also, the personal contact is performed directly by one of the investigators ([name] and [name]).

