11.4.2 Primary Analysis

At the end of the 31-day period making up the first part of the study, the datasets concerning the receptive fields are evaluated by the principal investigators ([name], [name]).

Here, next to the numerical tables exhibiting the monitored changes in size and position of the receptive fields, a graph will be made explaining the occurrence of these fields in relation to the time since the amputation occurred.

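### Onset of receptive fields after amputation is not observed under the plan as written, so the synopsis aims of incidence and timed occurrence reduce to cross-sectional presence by time since amputation

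*Combined protocol and SAP*

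**What the plan says.** The synopsis (Objectives) names, beside reliability, an aim to study the fields "as well as their incidence and changes over time". Its Outcomes row makes "their timed occurrence after the amputation of these receptive fields" part of the primary outcome. Section 3.1 repeats this as a question for part 1: "their timed occurrence after the amputation of these receptive fields as well as the inter-/intratester reliability in their detection".

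The people studied are existing amputees. The synopsis criterion is "Lower limb amputation (independently of side or height of amputation"), and 7.1 asks for "Lower limb amputation", consent and legal capacity. Neither limits time since amputation or requires fields to be present or absent at entry. Section 7.2 states: "The study participants are preselected through a database of the Rehaklinik Bellikon". Candidates are contacted by e-mail "or personally if stationary at the Rehaklinik Bellikon".

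Mapping takes place on days 1, 2, 7, 14, 21, 28 and 31, counted from enrolment. One tester maps on all days except 14 and 28, when a second tester does (9.2.1).

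The only planned analysis of occurrence is in 11.4.2: "a graph will be made explaining the occurrence of these fields in relation to the time since the amputation occurred". The example data sheet in 11.4.1 is made once for each detected field and has no entry for time since amputation. Sections 11.4.1 and 11.5 restrict the analysis to participants who complete as approved and exclude anyone who misses a whole meeting.

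**The concern.** Incidence and time of occurrence need a time origin, a set of people or sites at risk, and observation of the moment a field appears. Here the clock starts at enrolment, which may be weeks or many years after amputation. A field found on day 1 could have appeared at any time before, and a field that came and went before entry leaves no trace. Plotting presence against time since amputation compares different people at different distances from surgery. It does not follow anyone through the development of a field.

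At stake is one component of the synopsis's primary outcome, which the plan as written does not deliver, and the risk that the graph is taken for a natural history. A second weakness follows from the data layout. A participant with no detected field generates no sheet, so even a prevalence could lose its denominator.

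**Working it through.** **The plan's own figure.** There is none for incidence or timed occurrence. The sample size in 11.2 (28, raised to 31 for 10% dropout: 28 × 1.10 = 30.8) concerns change in size and position. I use 28 for completers and 31 for everyone mapped on day 1.

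**What a timing estimate needs, against what the plan provides.**
- *Time origin at amputation:* follow-up starts at enrolment.
- *Observed onset:* no history of onset is described. A day-1 field is left-censored at the time since amputation.
- *At-risk set and estimator:* none is defined.
- *A place among the outcomes:* the objectives (4.1 to 4.3), the outcomes (5.1, 5.2) and the hypotheses (11.1) mention neither incidence nor timed occurrence, and 5.3 says there are no other outcomes.

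**How much of the period after amputation is observed.** Day 1 to day 31 is 30/365.25 = 0.082 year. For someone *t* years after amputation at entry, the window is 0.082/(*t* + 0.082) of the time elapsed by day 31: 25% at 3 months, 7.6% at 1 year, 1.6% at 5 years, 0.8% at 10 years.

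**How much information there is on new onset.** Day-1 prevalence is not in the documents, so I assume 30%, 50%, 70% or 90% of 28. With *m* field-free participants:
- person-years = *m* × 30/365.25
- with no onsets, the upper limit of the exact two-sided 95% interval for 31-day risk = 1 − 0.025^(1/*m*)
- expected onsets at an assumed hazard *h* per year = *m* × (1 − exp(−*h* × 30/365.25))

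| Assumed prevalence | *m* | Person-years | Upper limit, 0 onsets | Expected onsets, *h* = 0.1 to 1.0 |
|---|---|---|---|---|
| 30% | 20 | 1.64 | 17% | 0.16 to 1.58 |
| 50% | 14 | 1.15 | 23% | 0.11 to 1.10 |
| 70% | 8 | 0.66 | 37% | 0.07 to 0.63 |
| 90% | 3 | 0.25 | 71% | 0.02 to 0.24 |

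These rows cover a person's first field only. The protocol works field by field (heel and forefoot separately), so someone with one field could still gain another.

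**What the design can give.** Exact (Clopper-Pearson) 95% intervals for day-1 prevalence: 8/28 = 29% (13% to 49%), 14/28 = 50% (31% to 69%), 20/28 = 71% (51% to 87%), 25/28 = 89% (72% to 98%). With all 31 in the denominator, 16/31 = 52% (33% to 70%). Splitting by time since amputation costs more: in four equal bands of 7 (my assumption; the plan has no bands), 4/7 has an interval of 18% to 90%.

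**The denominator.** Suppose 14 of 28 have a field. Sheets then exist for those 14 only, and every person in the dataset has a field: 14/14 = 100%, against a true 14/28 = 50%.

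**The case against.** A reader might infer that incidence cannot be estimated from this design at all, and that it yields prevalence only. The documents do not support that, for two reasons.

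First, seven mappings can reveal fields that appear after day 1, so a 31-day incidence is observable in principle. It would be imprecise, as the table shows. It would also be mixed with detection error: the reliability of detection is itself under study, and a field first found on day 14 or 28 coincides with a change of tester.

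Second, presence against time since amputation is current-status data. It can inform the distribution of onset if fields persist once present and if entry to the sample does not depend on field status. The plan states neither assumption and names no such method, and about 28 people is few for it. This is a gap in specification, not an impossibility. Inpatients may be enrolled, so recent amputees are possible, but nothing requires them.

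A reader might also infer that time since amputation is not collected. That does not follow. The graph in 11.4.2 needs it, and the case report form is a separate appendix that is not available here.

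It can fairly be said, too, that part 1 is declared descriptive, that sections 4 and 5 are already narrower than the synopsis, that the graph's description makes clear it is drawn against elapsed time, and that no time-to-event estimate is planned. That readers would mistake it for a developmental course is a prediction. These points limit the harm. They do not remove the mismatch, because the synopsis still calls timed occurrence a primary outcome.

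**Conclusion.** The concern holds in this form: onset after amputation is not observed under the plan as written, incidence and timed occurrence are undefined and missing from sections 4 and 5, and the planned graph shows cross-sectional presence by time since amputation. This conclusion rests on the eligibility, recruitment, schedule and analysis sections alone and needs no assumed figure.

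The size of the imprecision does rest on assumptions. With 3 to 20 field-free participants and no onsets, the upper limit for first-field risk over 31 days is 71% to 17%. At hazards of 0.1 to 1.0 per year, the whole study would expect about 0.02 to 1.6 first-field onsets. Overall prevalence would be known to within about 19 points either side at 50%.

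The analyses of change in size and position, the sample size and the numbered hypotheses are not affected.

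**What to change.** 1. In the synopsis, replace incidence, and in the synopsis and 3.1 replace timed occurrence after amputation, with *prevalence of receptive fields at day 1 by time since amputation (cross-sectional)*. List this outcome consistently in section 5.
2. In 11.4.2, describe the graph as cross-sectional prevalence by time since amputation, with exact 95% intervals.
3. In 11.4.1, add a participant-level record holding time since amputation (if the case report form does not already have it) and field presence on day 1, yes or no. Adding a column to the existing sheets would not be enough, since a field-free participant has no sheet.
4. For this summary, use everyone mapped on day 1 as the denominator, including field-free participants and later dropouts. State that the completer and missed-meeting rules of 11.4.1 and 11.5 do not apply to it.
5. Report fields first found after day 1 as counts only, by tester.

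The cost is a narrower claim and a little more analysis work. No extra participants or visits are needed.

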	(Streuung) between	similar population sub	ogroups (chronic pain		
	patients) is of 0.27%.				
	Therefore, the effect size is d = 1.11 with μ_i = 0.3 and SD = 0.27.				
	We set the significant	ce level at 5% and the p	power at 0.8.		
	Using the paired t-tes	t these values originate	e the following N's:		
	μ _i	d	Ν		
	0.25	0.93	40		
	0.3 1.11 28				
	0.35 1.23 24				
	As we assume a dropout rate of 10% we aim at 31 Participants for				
	the duration of this st	udy.			
Study Duration:	For each subject, the	study lasts about 5 to 6	6 weeks.		
Study Schedule:	First subject: 24.10.2	017			
	Last subject: 08.05.2018				
Investigator(s):	[name],				
	Sportmedizin und Re	habilitation			
	[name]				
Study Centre(s):	Rehaklinik Bellikon				
	[name]				

Statistical	ical Statistical Analysis:				
Considerations:	The statistical analy and "Excel".	ysis is performed wi	th the program "R"		
	For the primary outcome, the pictures are evaluated for size and position with the computer program "Photoshop". We define a change in size if a difference of more than 10% is detected in comparing a receptive field of two measurements. We define a change in position if the summed area of the two overlapping receptive fields exceeds the area of the bigger of the two single receptive fields by more than 20%. So, if the two receptive fields overlap completely (even if different in size) we do not count it as a change in position (only change in size).				
	For the secondary parameters of 10 rur compared between th	outcomes; a mean fo ns of gait analysis is c ne two randomized proto	or every one of the reated. These data is ocols (A and B).		
	All the results are tre 0.05 is achieved.	ated as significant if th	e significance level of		
	Power Analysis/Sam	nple size:			
	As this study is a first in this field (Pilot), regarding literature is not present and different assumptions (professional guesses) must be made.				
	We define a change is the size change is of We anticipate a change receptive fields betwee the purposes of our means that the attach the receptive field any From previous studi (Catley M. J. (2014 (Streuung) between patients) is of 0.27%.	n size of the receptive fi more than 10%. ge in size or position of en day 1 and 31 to be and further studies. In red electrodes at day 1 (more at day 31. es concerning the tw 4)) we know that the similar population sub	ield if over the 31 days 30% of the measured clinically significant for a this case significant would not be touching o-point discrimination e standard deviation ogroups (chronic pain		
Therefore, the effect size is d = 1.11 with μ_i = 0.3 and SD =					
	We set the significance level at 5% and the power at 0.8.				
	Using the paired t-tes	t these values originate	e the following N°s:		
	μ _i	u 0.03	10		
	0.20	1 11	28		
	0.35	1 23	24		
		out rate of 10% we air	at 31 Participants for		
	the duration of this study.				

GCP Statement:	This study will be conducted in compliance with the protocol, the current version of the Declaration of Helsinki, the ICH-CCP or ISO
	EN 14155 (as far as applicable) as well as all national legal and
	regulatory requirements.

ABBREVIATIONS

AE	Adverse Event
CA	Competent Authority (e.g. Swissmedic)
CEC	Competent Ethics Committee
CRF	Case Report Form
ClinO	Ordinance on Clinical Trials in Human Research (in German: KlinV, in French: OClin)
eCRF	Electronic Case Report Form
CTCAE	Common terminology criteria for adverse events
DSUR	Development safety update report
GCP	Good Clinical Practice
IB	Investigator's Brochure
Но	Null hypothesis
H1	Alternative hypothesis
HFG	Humanforschungsgesetz (Law on human research)
HMG	Heilmittelgesetz
HRA	Federal Act on Research involving Human Beings
IMP	Investigational Medicinal Product
IIT	Investigator-initiated Trial
ISO	International Organisation for Standardisation
ITT	Intention to treat
KlinV	Verordnung über klinische Versuche in der Humanforschung (in English: ClinO, in French OClin)
LPTh	Loi sur les produits thérapeutiques
LRH	Loi fédérale relative à la recherche sur l'être humain
MD	Medical Device
OClin	Ordonnance sur les essais cliniques dans le cadre de la recherche sur l'être humain (in German : KlinV, in English : ClinO)
PI	Principal Investigator
SDV	Source Data Verification
SOP	Standard Operating Procedure
SPC	Summary of product characteristics
SUSAR	Suspected Unexpected Serious Adverse Reaction
TMF	Trial Master File

STUDY SCHEDULE

Pre-Study	1) Screening for suitable candidates at Rehaklinik Bellikon	2) Enrollment and signing of informed consent if suitable candidate
------------------	--	--

Phase 1 (Assessment of primary outcome, 7h)

	Day 1	Day 2	Day 7	Day 14	Day 21	Day 28	Day 31
Testing recepive fields (ca. 1h)	1x	1x	1x	1x	1x	1x	1x
Tester	A	А	А	В	Α	В	A
Time of day	х	Х	х	Х	х	х	х

